### **7. IMPLANT RETRIEVAL AND ANALYSIS OF REMOVED IMPLANTS (if applicable)**

**Explanted devices should be returned to Biomet and may not be sent to any other laboratory facility.** If your facility has the capacity to decontaminate the device prior to shipping, this is advised. If your device has not been decontaminated, you must ensure that all mailing instructions regarding biohazardous material are followed when returning the device to Biomet. The address for return of the item is:

Biomet Manufacturing

Attn: Clinical Research

**8. STATISTICAL ANALYSIS****8.1. SAMPLE SIZE JUSTIFICATION**

A. The primary goal of this study is to determine whether subjects receiving a Vanguard XP knee would feel more “normal/asymptomatic” than subjects who are implanted with a Vanguard CR knee. This will be achieved using Pearson Chi-Square test for two independent proportions.

Fixed Scenario Elements	
Distribution	Asymptotic normal
Method	Normal approximation
Number of Sides	2
Null Proportion Difference	0
Group 1 Proportion	0.66
Group 2 Proportion	0.83
Alpha	0.05

B. Based on these assumptions, 137 patients will give 90% power to detect a 17 percent difference between groups with regard to the percentage of patients who report their knee as feeling “normal”. We increase our sample size by 10% to allow for patients who do not follow up for various reasons. This gives a sample size of 153 for each group and a total of 306 patients.

**8.2 ANALYSIS OF THE PRIMARY STUDY ENDPOINT**

The statistical test used in the primary analysis will be a two-sided Pearson’s chi-square test for the difference in independent proportions. The null hypothesis will be rejected if  $p < 0.05$  for this test.

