### STUDY SUMMARY

TITLE	Randomized Controlled Clinical Outcomes of the Vanguard XP Bicruciate Knee System
DESIGN	Prospective Controlled Multi-Center
PURPOSE	Compare the clinical outcomes of the Vanguard XP Bicruciate Total Knee System to the Vanguard CR Total Knee System
OUTCOME MEASURES	Patient Perception of recovery, Operative Room Procedure Time, Intraoperative complications; Anterior Cruciate Ligament (ACL) status; knee stability; readmissions, adverse events, pain, patient satisfaction, quality of life
POPULATION	306 knees, 5 surgeons
ELIGIBILITY	Patients will be included according to FDA cleared labeling of device in accordance with indications and contraindications for use.
DURATION	The study is anticipated to last no longer than 12 years which will include time for enrollment, data collection through ten years of follow-up and data analysis.

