**2.3. NUMBER OF SITES AND SUBJECTS/PROCEDURES**

A total of 306 cases (knees) will be included in this study from four centers; 153 Vanguard CR and 153 Vanguard XP. Sample size calculation is provided in Section 8.1.

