**2.4. RANDOMIZATION**

Patients will be randomized using a 1:1 blocked randomization scheme. Bilateral patients should be randomized by knee. Randomization will occur by enrolling the patient into Joint Assist and assigning an operative date. At that point the electronic database will assign the treatment group for the patient. The patient will be blinded from treatment until surgery has occurred.

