**2.5. PRIMARY AND SECONDARY ENDPOINTS**

- A. Primary Endpoint: Percentage of patients reporting their knee feels “normal”.
- B. Secondary Endpoints: Patient Reported Outcome Measures “PROMs”, Knee Society Score, Complication Rate, Pain Relief, Functional outcomes, Survivorship

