**3.1. INCLUSION CRITERIA**

Subjects will be considered for inclusion in this trial if they satisfy the following study criteria\* and FDA cleared indications for use:

- A. Cemented application of components\*
- B. Bilateral subjects randomized by knee\*
- C. Patients with pre-existing contralateral knee surgery\*
- D. Painful and disabled knee joint resulting from osteoarthritis, rheumatoid arthritis or traumatic arthritis where one or more compartments are involved.
- E. Correction of varus, valgus, or posttraumatic deformity
- F. Sufficient soft tissue surrounding the knee, including the Anterior Cruciate Ligament.

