**8.3 ANALYSIS OF BASELINE, SAFETY, AND SECONDARY EFFICACY STUDY DATA****MODELS FOR CONTINUOUS MEASURES**

Comparisons of Vanguard XP vs Vanguard CR with regard to continuous baseline, safety, and secondary outcomes will be performed using standard statistical tests and will be chosen as appropriate for the scale and distribution of the measures being analyzed. A t-test, Wilcoxon test, or one-way ANOVA (as appropriate) will be performed to assess differences.

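### Bilateral patients are randomized by knee, but the primary test treats all knees as independent and the plan does not settle whether its unit is the knee or the patient

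*Combined protocol and SAP*

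**What the plan says.** - **Randomization and eligibility.** Section 2.4 says "Bilateral patients should be randomized by knee", under a 1:1 blocked scheme of unstated block size. Section 3.1 B lists "Bilateral subjects randomized by knee".
- **Target counted in knees.** The Study Summary gives "306 knees, 5 surgeons". Section 2.3 says "A total of 306 cases (knees) will be included in this study from four centers", 153 per device, and refers to 8.1 for the calculation.
- **Target counted in patients.** Section 8.1 ends with "This gives a sample size of 153 for each group and a total of 306 patients". Section 2.5 defines the primary endpoint as "Percentage of patients reporting their knee feels" normal.
- **Primary test.** Section 8.2 fixes a two-sided Pearson "chi-square test for the difference in independent proportions" at the 0.05 level and offers no alternative.
- **Secondary tests.** Section 8.3 selects by scale and distribution. For continuous measures, "A t-test, Wilcoxon test, or one-way ANOVA (as appropriate) will be performed to assess differences"; for categorical ones, Fisher's exact or the likelihood ratio chi-square. None of these is described as paired or clustered.
- **Person-level data.** Section 2.7 F puts EQ-5D in the PROMs questionnaire, and Section 2.8 B times visits from the date of surgery. Sections 2.7 G and 3.4 D record readmissions and deaths with their relation to the device. No section assigns such data to an arm when one person has a knee of each device.

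**The concern.** 306 knees equal 306 patients only if nobody contributes two knees, and the protocol expressly allows two. Two knees of one person share age, weight, activity and a way of answering questionnaires, so their outcomes are correlated. A test that assumes independent proportions ignores this, and the direction of the error depends on how often the two knees receive the same device. Because the unit is not stated, an analyst could also choose between all knees, patients, or one knee per patient after seeing the data.

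A related gap concerns measures that describe the person. If EQ-5D is compared knee by knee, a patient with one XP and one CR knee enters a score in each arm. Once both knees are done, that score reflects both devices and pulls the comparison toward no difference.

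**Working it through.** **1. The plan's own figure.** From 8.1: proportions 0.66 and 0.83, two-sided 0.05, 90% power. The pooled normal formula gives

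n = [1.960 × √(2 × 0.745 × 0.255) + 1.2816 × √(0.66 × 0.34 + 0.83 × 0.17)]² / 0.17² = 136.05, so 137 per arm.

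137 / 0.90 = 152.2, so 153 per arm and 306 in total. The figures reproduce exactly. They assume one independent observation per unit.

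**2. How many people 306 knees could be.** Patients = 306 − (bilateral knees)/2. With an assumed 10%, 20% or 40% of knees from bilateral patients, this is about 291, 275 or 245. The 40% value is a stress case, because every enrolled knee needs a functional ACL (Section 1.2).

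**3. Effect on the primary test.** The true null variance relative to the Pearson variance is

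ratio = 1 + share × (2 × match − 1) × phi.

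Here share is the proportion of knees from bilateral patients, match is the probability that both knees get the same device, and phi is the within-person correlation of the yes/no outcome. True type I error is 2 × [1 − Φ(1.96/√ratio)]. None of the three inputs is in the documents, so they are assumed:

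- match is 0.50 for independent assignment; 0.42, 0.37 and 0.25 for blocks of 6, 4 and 2 with the two knees consecutive; 0 if the second knee always gets the other device;
- phi is 0.175, 0.385 or 0.628 at a common rate of 0.745, for latent correlations of 0.30, 0.60 and 0.85.

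Type I error from the formula at phi = 0.385:

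| Share | match 0.50 | match 0.37 | match 0.25 | match 0 |
|---|---|---|---|---|
| 10% | 5.0% | 4.9% | 4.8% | 4.6% |
| 20% | 5.0% | 4.8% | 4.6% | 4.1% |
| 40% | 5.0% | 4.6% | 4.1% | 3.3% |

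Worked cell: share 20%, match 0.37 gives 1 + 0.20 × (−0.26) × 0.385 = 0.980, hence 4.8%. The most extreme case (40%, match 0, phi 0.628) gives a ratio of 0.749 and 2.35%; simulation gives 2.36%.

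**4. Simulation.** 274 evaluable knees, latent correlation 0.30–0.85, common rates 0.66, 0.745 and 0.83, 40,000 runs per null setting (standard error 0.11 points) and 10,000 per power setting:

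| | Independent or blocks of 2–6 | Always opposite |
|---|---|---|
| Pearson type I, 10% share | 4.4–5.2% | 4.4–4.9% |
| Pearson type I, 20% share | 4.2–5.2% | 3.5–4.7% |
| Pearson type I, 40% share | 3.6–5.2% | 2.3–4.4% |
| Pearson power, 66% v 83% | 89.8–91.7% | 90.5–93.2% |
| Patient-clustered power | 89.9–93.2% | 91.0–96.4% |

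The patient-clustered test has type I error of 4.9–5.4% over all 135 null settings, about 4.8–5.6% allowing for Monte Carlo error. With no bilateral patients, Pearson gives 4.9% and the clustered test 5.1%.

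**5. EQ-5D.** If both knees are done before the score is taken, a patient with one knee of each device carries no contrast. A knee-level difference then shrinks by share × (1 − match). At 20% this is 0.20 × 0.50 = 10% to 0.20 × 0.75 = 15%; at 10% it is 5–8% and at 40% it is 20–30%. If the first knee's visit precedes the second operation, it is about half. Power at 20% share and blocks of 4, assuming a 0.35 SD effect, half of it from each device once both knees are done, and correlation 0.8 between one person's staged scores:

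| EQ-5D analysis | Scores reflect both devices | First visit precedes second operation |
|---|---|---|
| Knee level | 72.3% | 77.6% |
| Without patients assigned different devices | 75.5% | 75.0% |
| All patients, by first knee's device | 72.1% | 78.1% |

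Neither one-record analysis is better under both timings.

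**The case against.** The strongest reply is that the mismatch is loose wording. Section 2.3 counts knees and sends the reader to 8.1, Sections 2.4 and 3.1 make the knee the randomized unit, and the endpoint in 2.5 speaks of the patient's knee. Under independent assignment the Pearson variance is exactly right on average, under blocks it errs on the safe side, and the power claim survives. All of this stands, and it is why the point is minor. It does not supply a method for paired knees. The latitude in 8.3 concerns scale and distribution, not dependence, and 8.2 gives none.

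It is also fair that Section 2.7 F only lists EQ-5D in a questionnaire about the knee replacement. That EQ-5D describes the person rests on quality of life being a listed outcome in the Study Summary and on the EQ-5D reference in Section 16, whose title concerns health status. The EQ-5D figures describe assumed models, not this trial. Recording relation to the device (2.7 G, 3.4 D) partly handles attribution of events, but not those unrelated to either knee.

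Two stronger readings are tempting. A reader might infer inflated false positives: if both knees of every pair shared an arm, type I error would be about 5.3–7.5% (10–30% of knees, correlation 0.3–0.7). By-knee randomization does not allocate that way. A reader might also infer that 306 is too small, because one knee per patient would cut power to 88.9–81.5% with 5–30% of patients bilateral. The plan does not prescribe that analysis, and with all knees analysed the stated power holds.

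**Conclusion.** The point holds as a minor one. The unit of analysis is inconsistent across sections, and the fixed primary test ignores within-patient correlation. No inflation of false positives is expected, and 137/153 per arm needs no change. The cost of leaving the test as it is would be slight conservatism and a little lost power, negligible when few patients are bilateral. It becomes material only with a high bilateral share, strong correlation and a tendency toward different devices.

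For EQ-5D, a knee-level comparison would be diluted by roughly 5–15% at a 10–20% share with independent or small-block assignment if scores reflect both devices, and by about half that under staged timing. All sizes rest on assumed share, correlation, block size, second-knee rule and timing of surgery. The missing rule itself is plain from the text.

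**What to change.** - **Unit.** In 2.5, 8.1 and 8.2 state the knee as the unit, change 306 patients to 306 knees, and note that 137/153 per arm assumes independent knees.
- **Primary test.** In 8.2 compare the proportion of knees reported as normal by assigned device, with patient as cluster: GEE with independence working correlation and robust standard error, or a cluster-adjusted chi-square. Use the same clustering for knee-level outcomes in 8.3.
- **EQ-5D.** Use one record per patient. Pre-specify both an all-patient analysis by the device assigned to the first enrolled study knee, and an analysis without patients whose two enrolled knees were assigned different devices. Counting only enrolled knees avoids ambiguity when a second knee is randomized but screen-fails before the first bony cut (3.3 B). Which analysis is the main one is the sponsor's choice, since the better one depends on the timing of the two operations.
- **Person-level events.** Count deaths, and readmissions not related to one knee, once per patient, and show patients with one knee of each device as a separate row.

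**Cost.** Wording and one standard procedure, with no new data and no extra knees. The clustered test can run slightly above 5% (up to about 5.6%). The restricted EQ-5D analysis would omit about 14–20 patients at a 20% share: 27 pairs × (1 − match) for match 0.50 to 0.25, or all 27 if devices are always opposite.

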**8.3 ANALYSIS OF BASELINE, SAFETY, AND SECONDARY EFFICACY STUDY DATA****MODELS FOR CONTINUOUS MEASURES**

Comparisons of Vanguard XP vs Vanguard CR with regard to continuous baseline, safety, and secondary outcomes will be performed using standard statistical tests and will be chosen as appropriate for the scale and distribution of the measures being analyzed. A t-test, Wilcoxon test, or one-way ANOVA (as appropriate) will be performed to assess differences.

**CATEGORICAL DATA ANALYSES**

Comparisons of Vanguard XP vs Vanguard CR with regard to categorical baseline, safety, and secondary outcomes will be performed using standard statistical tests and will be chosen as appropriate for the scale and distribution of the measures being analyzed. Specifically, categorical outcomes will be compared for investigational and control groups using the Fisher's Exact test (for 2x2 tables with small sample sizes that do not satisfy assumptions for likelihood ratio chi-square test) or the Likelihood Ratio chi-square test.

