### **1.4. PURPOSES**

- A. Compare patient perception of their knee implant feeling “normal / asymptomatic.”
- B. Compare clinical outcomes through 2 year standard of care follow-up.
- C. Evaluate patient perceived clinical outcomes and survivorship through 10-years of follow-up.

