**F. Clinical Outcomes**

1. Data to determine the clinical and functional performance of the device will be collected. Pre-operative and post-operative analysis will be compared using recognized and validated systems:
  - a. **Modified Knee Society Score**
    - i. The American Knee Society Score is part clinical exam and part patient administered assessment of the knee. The objective part of the score, also known as the "knee score," should be collected in the clinic by qualified personnel. The functional and pain scores can be collected in

the clinic or via phone or mailer. An additional assessment of the incidence of “anterior knee pain” has been added to this CRF as an exploratory endpoint but does not affect the score. The full score will be collected preoperatively and at each post-operative visit through 2-years. After the 2-year visit, the patient administered portion will be collected with the PROMS Questionnaire by phone, email, or mailer from the patient.

b. Patient Reported Outcome Measures “PROMS”

- i. A PROMS Questionnaire will be completed by the patient before surgery, and at each postop appointment indicated in the data collection table to assess the patient’s perception of their knee replacement. This survey can be collected in the office, over the phone, or via mailer. The preoperative questionnaire contains the SANE, EQ-5D, Oxford Knee Score, and KOOS (The FJS and Patient Satisfaction questionnaires are only completed post-operatively). The postoperative questionnaire contains the SANE, Patient Satisfaction, FJS, EQ-5D, Oxford Knee Score, and KOOS validated patient administered outcomes scores.

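### Section 8.3 names no analysis that adjusts for the pre-operative score, which costs precision, and the plan gives no method for 10-year survivorship

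*Combined protocol and SAP*

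**What the plan says.** Section 8.3 is the only analysis text for secondary outcomes. For continuous measures it states: "A t-test, Wilcoxon test, or one-way ANOVA (as appropriate) will be performed to assess differences". For the rest, "categorical outcomes will be compared for investigational and control groups using the" Fisher's exact test when samples are small, or otherwise the likelihood-ratio chi-square test. The choice among standard tests is left to suit the scale and distribution of each measure.

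Pre-operative values exist for most scores. Section 2.7 F says of the KSS: "The full score will be collected preoperatively and at each post-operative visit through 2-years". Of the patient-reported measures it says: "The preoperative questionnaire contains the SANE, EQ-5D, Oxford Knee Score, and KOOS". The Forgotten Joint Score and patient satisfaction are post-operative only. The same section adds: "Pre-operative and post-operative analysis will be compared using recognized and validated systems". No section says whether the comparison of Vanguard XP with Vanguard CR uses the post-operative score, the change, or an adjusted score.

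The secondary endpoints in Section 2.5 include "Knee Society Score, Complication Rate, Pain Relief, Functional outcomes, Survivorship". Section 1.4 gives purpose B as "Compare clinical outcomes through 2 year standard of care follow-up" and purpose C as "Evaluate patient perceived clinical outcomes and survivorship through 10-years of follow-up". Section 15 defines revision, removal and reoperation, and Section 2.7 G points to Sections 4 and 15 for revisions and removals. No section says which of these ends survivorship, how it is estimated, or how knees with incomplete follow-up are handled. Section 9 deals with data entry, reimbursement and telephone follow-up, not with analysis.

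**The concern.** A pre-operative score that correlates with the post-operative score explains part of the variation between patients. An analysis that ignores it gives wider intervals than the data allow. A change-score analysis uses it, but inefficiently unless the correlation is high. With five instruments measured before surgery and the choice between post-operative score and change left open, the analyst would also be choosing after the data are in.

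For survivorship, death and withdrawn consent end follow-up (Section 3.4 D) and withdrawn patients are not replaced (Section 3.4 A), so some knees will have partial follow-up by 10 years. None of the tests named in Section 8.3 can use partial follow-up. Without an event definition and a censoring rule, the 10-year figure for each device depends on which denominator is picked.

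**Working it through.** **The plan's own figure.** Section 8.1 uses 0.66 and 0.83, two-sided alpha 0.05 and 90% power.

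n = [1.960 × √(2 × 0.745 × 0.255) + 1.2816 × √(0.66 × 0.34 + 0.83 × 0.17)]² / 0.17² = 136.05, rounded up to 137 per group (power 0.902). Then 137 / 0.9 = 152.2, rounded up to 153 per group, or 306 in total. The plan's numbers reproduce. They concern the primary endpoint only; no figure is given for any Section 8.3 analysis.

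**Scores.** Let r be the correlation between pre- and post-operative scores. The documents give no value, so 0.3 to 0.7 is an assumed range, with equal variances at both times. The relative variance of the between-arm difference is 1 for the post-operative score, 2(1 − r) for change, and 1 − r² for ANCOVA. The saving is therefore r² against the post-operative score and (1 − r)/2 against change.

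| r | Change | ANCOVA | Saving vs post-operative score | Saving vs change |
|---|---|---|---|---|
| 0.3 | 1.40 | 0.91 | 9% | 35% |
| 0.5 | 1.00 | 0.75 | 25% | 25% |
| 0.7 | 0.60 | 0.51 | 49% | 15% |

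With 137 per arm, two-sided 0.05 and 80% power, the detectable difference is (1.960 + 0.842) × √(2v/137) SD, where v is the relative variance. That is 0.338 SD for the post-operative score, and 0.323, 0.293 and 0.242 SD for ANCOVA at the three values of r.

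**Survivorship.** Assume constant hazards, a true 10-year risk R and 153 knees per arm. Set λ = −ln(1 − R)/10, and let a be the yearly attrition hazard. If no attrition is death:

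- revised over all knees = λ/(λ + a) × [1 − exp(−10(λ + a))]
- revised over knees with known status = that figure / (that figure + exp(−10(λ + a)))

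The 10% allowance in Section 8.1 has no time horizon. Spread over 10 years it gives a = −ln(0.9)/10 = 0.0105. For R = 10%, λ is also 0.0105. All knees reads 0.5 × (1 − 0.81) = 9.5%, and known status reads 0.095/(0.095 + 0.81) = 10.5%.

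| Assumed R | Attrition | All knees | Known status |
|---|---|---|---|
| 10% | 10% in total | 9.5% | 10.5% |
| 5% | 10% in total | 4.7% | 5.3% |
| 10% | 5% a year | 7.9% | 12.6% |
| 5% | 5% a year | 3.9% | 6.4% |

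The standard error per arm is √(0.10 × 0.90/153) = 2.4 points at 10%, and 1.8 points at 5%. If half of the 10% attrition is death, the target for R = 10% becomes a cumulative incidence of 9.7%, and either crude figure is within about 0.2 points of it. Five per cent a year is an assumption from outside the plan. It means 1 − exp(−0.5) = 39% lost over 10 years, none of it by death, so the last two rows are an upper bound.

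All of these figures treat knees as independent, although Section 2.4 randomizes bilateral patients by knee.

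**The case against.** The strongest reply on the scores is that the named tests are valid under randomization, that Section 8.3 leaves room to choose, and that no power target is set for any score, so nothing stated fails. The first part stands: a reader might infer that the planned comparisons are biased, and they are not. The freedom to choose does not supply a method, though. A gain in precision from data already collected needs no missed target to be worth taking.

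On survivorship, a reader might infer that the plan will test 10-year failure with a chi-square test. The documents do not say so. Section 8.3 governs comparisons between the two devices, purpose C says survivorship is to be evaluated rather than compared, and no section treats it as a yes/no outcome. The gap is silence, not a wrong test. A reader might also infer that unequal loss between arms would inflate false positives. The documents assign no test to survivorship and give no loss rates by arm, so that is not supported. It is also fair that post-2-year contact by telephone, mail or email may hold loss down, and that at the plan's own allowance the distortion is minor.

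**Conclusion.** The main point holds as an improvement at almost no cost. Adjusting for the pre-operative score would reduce variance by 9% to 49% against a post-operative test and by 15% to 35% against a change test, for assumed r between 0.3 and 0.7 and equal variances. It affects precision only, and only the KSS, SANE, EQ-5D, Oxford and KOOS.

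The survivorship point holds as a smaller gap in specification. At the plan's attrition allowance a crude figure would be off by at most about 0.5 points, against a standard error of 2.4. Larger shifts appear only under the assumed 5% yearly non-death loss.

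A separate contradiction bears on who is followed. Section 15 I lists randomization failure after surgery has commenced as a withdrawal, while Sections 3 B and 3.3 B say such patients stay in follow-up and have data collected. These sections must be reconciled.

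**What to change.** In Section 8.3:

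1. Compare the KSS, SANE, EQ-5D, Oxford and KOOS between arms at each analysed follow-up time by ANCOVA with the pre-operative score as covariate. Name a rank-based version for scores that are clearly non-normal. The Forgotten Joint Score and satisfaction have no baseline and stay unadjusted.
2. Analyse survivorship by randomized arm as time from surgery to first revision or removal, as Section 15 defines them. Censor at last contact or withdrawal of consent, and treat death as a competing event. Report 10-year cumulative incidence per arm with a 95% confidence interval that allows for two knees from one patient.

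Separately, reconcile Section 15 I with Sections 3 B and 3.3 B.

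The cost is a few sentences and slightly more analysis work. Pre-operative scores are already collected, and dates of removal, metal-component revision and death are on the withdrawal form (Section 3.4 D). Partial revisions go on the adverse event form. The details listed for it in Section 6 include onset but not a procedure date; the form itself is not in the documents, so that field should be confirmed. The primary test and the 306 knees do not change.
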